
Procedures for MRI Scans (for a subset of 15 able-bodied individuals):

As stated above, the MRI scans will be obtained as part of a different IRB protocol. The IRB

protocols that we are requesting permission to use the brain MRI scans from are two protocols whose PI ([name]) is a co-investigator in the current IRB protocol: IRB00081268 (Noninvasive brain stimulation to evaluate neural plasticity after stroke) and IRB00072542 (Using concurrent brain imaging and stimulation to characterize brain behavior in stroke). The methods for the MRI will be as described in the above protocols, and for convenience are also listed here.

MRI acquisition: Scanning will be conducted at Emory University at the Center for Systems Imaging on a Siemens 3T Trio whole-body MRI scanner. A high-resolution T₁ scan (TR = 7.4ms, TE = 3.7ms, flip angle θ = 6°, FOV = 256mm, 160 slices, 1 mm thickness, scan time=3.2min) will be performed without contrast. The study team will have direct and immediate access to the data using Emory University's secure network server.

Risks

Risks associated with clinical testing, gait training, and motion analyses include falling, fatigue, poor heart rate and blood pressure response to walking and minor skin irritation from the adhesive tape. To minimize risk, subjects will wear a safety harness during the treadmill testing and will be given a rest break whenever requested. Heart rate will be monitored continuously and blood pressure will be monitored at rest breaks. If heart rate exceeds 80% of their age predicted heart rate maximum, walking will be stopped until it returns to baseline. If a subject's blood pressure exceeds 190/100 mmHg, the session will be stopped and their blood pressure will be continually monitored until it returns to baseline. The subject's primary or referring physician will be notified. Throughout the experiment, the experimenter has access to an emergency safety switch that can be used to stop the treadmill immediately. To ensure sufficient cardiovascular health to complete an intensive gait training program, stroke subjects who participate in 18 sessions of gait training (Cohort 1) will complete a cardiac exercise stress test.

Risks associated with electrical stimulation: After electrical stimulation to the ankle or knee muscles, subjects may experience some muscle soreness for about 2 days that is similar to the muscle soreness if someone lifts weights or exercises vigorously after a long break. During electrical stimulation, the potential for equipment malfunction is also present, which might result in burns to the skin. However, the equipment used is highly reliable and prolonged exposure necessary to cause the risk of skin damage is highly unlikely with the stimulation parameters used in this experimental design. Risks associated with measurement of spinal excitability using peripheral stimulation are similar to the risks associated with electrical stimulation listed here.

Risks associated with the use of TMS to assess corticospinal excitability: Seizures are a rare reported risk with TMS. The current study involves single-pulse TMS at low frequency (< 0.2 Hz), which has been used for over 20 years in a variety of normal subjects and in subjects with neurological conditions and has been found to be safe. Safety precautions and practice recommendations for TMS research are summarized in publications; and these guidelines will be followed in our current single-pulse TMS protocol.⁷⁷⁻⁸⁰ Based on a recent Consensus paper (meta-analysis / review of TMS literature), to date, more than 5000 research papers have been

published using single-pulse TMS; only 2 cases of seizures have been reported with single-pulse TMS⁸¹⁻⁸³. In addition, Gilbert et al showed that in 38 studies involving 850 subjects including children with cerebral palsy and other neurological conditions, there were no seizures or other major adverse events⁷⁷. Another recent review concluded that the safety of single-pulse TMS in clinical practice, including as an acute migraine headache treatment, is supported by biological, empirical, and clinical trial evidence⁸⁰. TMS rates used in our study, of 0.2 Hz or less, are safe in epileptic patients⁸⁴. However, to take additional steps to minimize risks, we will not include any individuals with a history of seizures in our study. In addition, during TMS, subjects may feel twitches in the muscles of arm, leg or face during the magnetic stimulation, but these twitches should not be painful. There is a rare possibility of headaches, scalp discomfort, dizziness, or light-headedness. If they occur, these effects are usually mild and short-lasting. Recently, a research of literature showed recent publications providing case reports of episodes of syncope or seizure during single-pulse TMS in able-bodied individuals⁸⁵⁻⁸⁷. To prevent the risk of syncope, vaso-vagal stimulation, or dizziness in the current study, we will exclude subjects if they have a history of syncope, dizziness, loss of consciousness, or nausea in the past 12 months, including but not limited to syncope triggered by drawing blood. Metal and conductive objects close to the coil may move during magnetic stimulation. A click during magnetic stimulation may be heard. The subjects may be provided with foam earplugs that can prevent any discomfort from this clicking noise. There is also a risk of mild skin redness or irritation at the location where the muscle sensors have been placed, but this will usually go away quickly after sensors are removed.

Risks associated with assessment of muscle strength include fatigue, muscle soreness, strains in the muscles surrounding the hip, knee, ankle or foot.

Potential Benefits

Although these procedures are experimental, and the responses of individual subjects to the gait training sessions may vary widely, the subjects may experience small and short-lasting increases in their walking speed, endurance, or balance as a result of these treatments. Also, the long-term findings of this study can help us better understand the effects of and guide the design of clinical rehabilitation which can benefit other stroke survivors in the future.

Type of Information Collected

During clinical testing, to help characterize the clinical characteristics of the subject group, information such as age, time since the stroke, height, weight, side of hemiparesis, etc. will be collected. To help characterize the level of impairment of the subject group, information such as walking speed, endurance, walking function score, lower extremity sensation, etc. will be collected. During motion analysis and gait training, the 3-dimensional camera system will be used to track the 3-D positions of the subject's segments; these data will be used to compute joint angles, ground reaction forces, joint moments, joint powers, etc. During strength testing, the force generated by the subject's joints will be measured. During assessment of corticospinal excitability via TMS, the EMG sensors attached to the muscles will record the level of muscle activity in response to the TMS pulses. All subject data will be de-identified and then compiled on an excel spreadsheet and imported into SPSS 14 (SPSS, Chicago, IL) for statistical analysis. De-identified data will be disseminated through group discussions, presentations and publications.

Management of Subject Data

Subjects will not be anonymous to the researchers. As a first step during data management, subject identities will be de-identified by assigning each subject a number. Any computer files containing information that link the identifiable subject data with the de-identified subject number will be password protected and stored on a secure Emory University computer. Only de-identified data will be used to compile spreadsheets of the various outcome measures collected as part of this study (joint angles, clinical impairment scores, EMG, etc.). De-identified data may be stored for future use until 5-years after completion of the study. All signed consent forms will be stored in the subject's folder (organized by de-identified subject numbers) in a locked file cabinet at the University. Participants will not be audiotaped, photographed or videotaped without their permission during this study.

6. Participant selection

We plan to collect data on a sample of 55 individuals post-stroke and 35 able-bodied individuals. However, we anticipate a withdrawal rate of ~10%. Therefore, we will recruit 60 subjects and 45 able-bodied subjects.

Inclusion Criteria for Post-Stroke Subjects are: 1) age 30-80 years, 2) chronic stroke (>6 months post stroke), 3) first (single) lesion, 4) ambulatory with or without the use of a cane or walker, 5) sufficient cardiovascular health and ankle stability to walk for 6 minutes at their self-selected speed without an orthoses, 6) resting heart rate 40-100 beats per minute, 7) resting blood pressure between 90/60-70/90.

Exclusion Criteria for Post-Stroke Subjects are: 1) evidence of moderate/ severe chronic white matter disease or cerebellar stroke on MRI, 2) cerebellar signs (ataxic ("drunken") gait or decreased coordination during rapid alternating hand or foot movements, 3) insulin dependent diabetes, 4) history of lower extremity joint replacement, 5) score of >1 on question 1b and >0 on question 1c on NIH Stroke Scale, 6) inability to communicate with investigators, 7) neglect/hemianopia, or unexplained dizziness in last 6 months, 8) neurologic conditions other than stroke, 9) orthopedic problems in the lower limbs or spine (or other medical conditions) that limit walking. Additional exclusion criteria for TMS (measurement of corticospinal excitability) are: 10) history of seizures, 11) metal implants in the head or face, 12) history of recurring or severe headaches/migraine, 13) headache within the past 24 hours, 14) presence of skull abnormalities or fractures, 15) hemorrhagic stroke, 16) history of dizziness, syncope, nausea, or loss of consciousness in the past 12 months.

Inclusion Criteria for Able-Bodied Individuals are: 1) age 21 to 80 years, 2) no history of neurologic disease, 3) no history of orthopedic disease or injury affecting the lower extremity.

Exclusion Criteria for Able-Bodied Individuals are: 1) history of neurologic disease, 2) history of orthopedic disease or injury to the lower extremity, 3) an implanted cardiac pacemaker. Additional exclusion criteria for the TMS portion of the study (corticospinal excitability measurement) are: 4) history of seizures, 5) metal implants in the head or face, 6) history of recurring or severe headaches/migraine, 7) headache within the past 24 hours, 8) presence of skull abnormalities or fractures.

Subject Recruitment. Study participants will be recruited from the general community within and outside Emory University.

Withdrawal from study. Participation in the present study will be voluntary and subjects will be able to opt out of the study at any time.

Our subject population will be representative of adult patients with stroke and healthy adults. The incidence of stroke is considered rare in children, estimated to be less than 13 cases per 100,000 children⁸⁸ and their inclusion would not provide additional information compared with the data gathered in adults.

7. Statistical analysis

Hypotheses testing will be done with a p-value set at 0.05. The outcome variables used for analyses will include peak knee and ankle flexion during walking, propulsive forces during walking, walking speed and endurance, peak and duration of EMG activation during walking, and TMS-derived measures of corticospinal excitability (peak EMG in response to TMS, motor threshold intensity, slope and peak of the TMS-recruitment curve). To test *H1*, for each of the variables, one-way repeated measures ANOVA will be performed to check for differences in the variable after versus before 18 sessions of training. To test *H2*, we will plot the dependent variable versus time (test session number). Using these plots, the time to plateau and the time when the variable first shows a positive within-session change (threshold time) will be determined. One way repeated measures ANOVA will be used to compare the time to plateau and threshold time among 3 variables – peak propulsion, peak TMS muscle response, and over ground walking speed. To test *H3*, a Pearson's correlation will be performed between the change in peak propulsion after training versus change in peak TMS muscle response after training. For the hypothesis involving within-session changes (*H4*), repeated measures ANOVA will be performed to compare the within-session percentage change for each variable between different rehabilitation strategies.

Power Analysis: The current protocol has been powered using the primary outcome measure of paretic propulsive force generation. Based on means and standard deviations from our existing pilot data, for each aim, a sample of 24 subjects will provide 80% power to detect a 4.2% difference in propulsive force between sessions with standard deviation of 6% at a two-sided alpha level of 0.05. After completion, the data from this study will be used to conduct systematic power analysis for other outcome variables, which will be utilized to design a larger-scale future study.

8. Adverse event reporting

We will notify the IRB of any adverse events that occur during the protocol.

10. Device information

Equipment for Motion Analysis and Gait Retraining: A 7-camera system will be used to collect motion analysis data (Vicon, Oxford, UK). Ground reaction forces during treadmill walking will be collected using a treadmill instrumented with two 6-component force platforms under each

belt (Bertec, USA). During over ground walking, ground reaction forces will be collected using a force plate embedded within the lab floor (AMTI, USA). In addition, small electromyography (EMG) sensors will be attached to various muscles to collect EMG data (Noraxon Inc., Arizona, USA). The EMG sensors will be attached using hypo-allergenic adhesive. Pressure-sensitive foot switches (25-mm diameter MA-153, Motion Lab Systems, LA) will be attached to the underside of the subjects' shoes; the foot switch data will be used to record gait events (Noraxon Inc, Arizona, USA). All these devices widely used for measurement of human movements.

Electrical Stimulation Equipment: Electrical stimulation will be delivered non-invasively via electrodes attached on the skin overlying the targeted muscle (ankle dorsi- and plantar-flexor muscles). Square electrical pulses of pulse durations upto 800- μ s, pulse amplitudes upto 150 Volts, and frequencies ranging from 1 to 100-Hz will be delivered. Electrical stimulation will be delivered using a Grass S8800 or S4800 stimulator (Grass Technologies Inc., RI, USA). To ensure subject safety, the stimulator will be used in conjunction with a transformer isolated, constant voltage SIU8T stimulus isolation unit which is designed to be used for research nerve and muscle constant voltage stimulation (Grass technologies Inc., RI, USA).

Transcranial Magnetic Stimulation Equipment: Magnetic stimulation will be delivered using a MagStim 200 unit (MagStim, Dyfed, UK). A custom bat-wing or double cone coil will be positioned over the scalp at the optimal site for activation of the target muscle. TMS is a safe and painless technique for investigating the excitability of neuronal tissue within the brain. In brief, a magnetic stimulus delivered via a coil held over the scalp is utilized to excite the neural tissue of the brain located beneath the coil. The coil is positioned appropriately to stimulate the area of the motor cortex that controls specific target muscles. Magnetic stimulators are commercially available, and the safety of their use with neurologically intact and neurologically impaired populations has been well documented. TMS has been utilized in several previous studies by the investigators including use with neurologic populations.

11. References and appendices

1. Heart disease and stroke statistics—2007 update. *A Report From the American Heart Association Statistics Committee and Stroke Statistics Subcommittee*. 2007

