As part of this protocol, study participants will participate in one of two cohorts. We will obtain systematic measurements of gait biomechanics (using 3-dimensional motion analyses), corticomotor excitability (using TMS), and walking function (using standard clinical tests of walking performance) through the course of 18 sessions of gait retraining (Cohort 1). In addition, we will investigate how different training strategies and parameters (such as electrical stimulation, fast walking speed, biofeedback) influence within-session and short-term improvements in gait biomechanics and corticomotor excitability (Cohort 2). A total of 35 individuals with stroke and 35 able-bodied individuals will be tested.

In addition to the data-collection described as part of cohort 1 and cohort 2 above, the study will also include 'pilot' or methodology-driven experiments on both able-bodied and stroke participants. These experiments do not include an intervention component and do not fall under the NIH definition of clinical trials. A majority of these pilot experiments will be conducted during the early or planning phase of the study. These pilot or methodological experiments will be utilized to test the measurement properties for the neurophysiological variables measured in the clinical trial, to evaluate short-term effects of the gait training or gait testing conditions, and to establish normative or reference values for able-bodied (as a control comparison for stroke) and stroke survivors (at baseline). The study procedures used for the pilot phase may be similar to those described for cohort 1 and 2, but only a subset of outcomes or tests may be included in the pilot phase, and a shorter duration experiment may be performed (e.g. 1 session instead of multiple evaluation or training sessions). These pilot phase data may contribute to scientific publications that inform our understanding of how methodological parameters such as posture (standing, seated), stimulation intensity, muscle state (active, rest), or timing (inter-stimulus interval between brain and nerve stimulation) influence the neurophysiologic measurements derived during non-invasive stimulation.

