The overall purpose of this protocol is to assess the biomechanical and neurophysiologic effects of rehabilitative strategies and protocols that are commonly used during physical therapy treatment of gait disorders post-stroke. As part of this protocol, 45 able-bodied individuals and 55 individuals with chronic stroke will be assigned to either Cohort 1 or Cohort 2, and will participate in 1-18 gait training sessions. If interested, study participants can also complete both study cohorts sequentially (with at least 3-weeks duration between switching from one cohort to the second). Evaluations for obtaining outcome measures will comprise clinical testing, muscle evaluations, gait analysis, and assessment of spinal and corticospinal excitability. Within Cohort 1 (stroke and able-bodied), 25 subjects will receive identical treatment throughout the training sessions (i.e. FastFES training). Within Cohort 2, 25 subjects will receive different rehabilitation strategies individually or in combination during each training session (e.g., treadmill walking, functional electrical stimulation, bio-feedback or verbal feedback about targeted walking parameters, split-belt walking, etc.). During gait training, Cohort 1 subjects will typically participate in a minimum of 2 and a maximum of 3 sessions per week. Subjects in Cohort 2 can participate in 1 to 18 gait training sessions but the frequency of the gait sessions can be varied according to the subject's and laboratory schedule (i.e. variable durations between consecutive sessions).

Aims

The aims of this protocol are to:

- 1) Study the changes in gait biomechanics, corticospinal excitability, and walking function during 18 sessions of gait retraining (Cohort 1).
- 2) Systematically determine the effect of parameters such as walking speed (slow, fast, variable, split-belt walking), functional electrical stimulation parameters (short-term changes induced by fast versus FastFES, stimulation intensity, number of muscles stimulated), and bio-

[figure not shown]
feedback on within-session changes in gait biomechanics, walking function, and corticospinal excitability (Cohort 2).

Hypotheses of the study

- By utilizing data collected on cohort 1 of subjects who undergo 18 sessions of FastFES gait retraining, the following hypothesis will be tested:

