 - H1.* Eighteen sessions (6-8 weeks) of gait training comprising fast treadmill walking and functional electrical stimulation (FastFES) will result in Improvements in gait biomechanics, corticospinal excitability, and walking function.
 - H2.* Improvements in gait biomechanics will precede the improvements in corticospinal excitability and walking function.
 - H3.* Improvements in walking function will be correlated to improvements in corticospinal excitability.
- By utilizing data collected on cohort 2 of subjects who receive different rehabilitation strategies during each training session, we will analyze short-term changes induced by 1-3 sessions of gait retraining to test the following hypothesis:
 - H4.* The magnitude of improvements in gait biomechanics and corticospinal excitability will be greater for gait training sessions that comprise:
 - walking at a faster versus slower speed
 - walking with versus without FES, i.e. Fast versus FastFES
 - walking with FES delivered to two versus one muscle during gait
 - walking with 2 belts going at different speeds or directions versus regular treadmill walking
 - walking with versus without visual bio-feedback or other feedback (e.g. verbal, tactile) about targeted parameters during gait
 - greater dosages (# of walking steps per session) of walking practice
 - combination of 2 strategies versus a single rehabilitation strategy

5. Study design and methods

Research Procedures

Flowchart showing the overview of study procedures.

The overall goal of this protocol is to provide novel insights into the biomechanical and neural mechanisms underlying gait rehabilitation. To achieve this goal, a series of experiments will be performed on young able-bodied individuals as well as stroke survivors. The protocols to be tested and procedures to be used are described in detail here. For all the procedures and sessions described below, all testing procedures will be explained to the subject at the beginning of each testing session. Also,

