during these testing procedures, rest breaks will be provided to the subjects as needed and as requested by the subject. Please see the adjoining flowchart for a summary of the procedures that subjects in each study cohort will undergo. Subjects will not be randomized to the 2 cohorts. Assignment to the cohorts will be based on the lab/personnel and subject schedules. A subject can participate in the 2 cohorts sequentially. Also, participants in Cohort 2, when testing hypotheses comprising a repeated-measures comparison of different gait training strategies (e.g. Hypothesis 4a evaluating effect of walking speed; Hypothesis 4b comparing FastFES versus Fast), participants may cross-over between strategies within or across gait sessions.

1) Medical Clearance:

If a subject shows interest in participation in cohort 2 of the study (18 training sessions), before participation, we will obtain written medical clearance from the subject's physician (See attached Medical Clearance form). In addition, the subject will undergo clinical assessment to confirm that they are eligible for study participation.

2) Procedures for Clinical Assessment of Walking Function and Muscle Strength:

All subjects will review and sign consent forms before clinical testing. Clinical Testing will be performed by a licensed physical therapist. Clinical testing may comprise: (1) measurement of subjects' over ground self-selected (SS) walking speed (6-meter walk test); (2) over ground walking endurance measured by the distance ambulated during the 6-minute walk test; (3) assessment of gait and dynamic balance (measured using the functional gait assessment, 4-square step test, and the Berg balance score); (4) lower extremity portion of the Fugl-Meyer score⁷⁰; (5) step activity monitoring; (6) lower extremity proprioception (in which each limb segment will be flexed or extended approximately 10 degrees and the subject will be asked to identify whether the limb is moving and in what

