Burst superimposition during muscle strength testing: A technique called the burst superimposition technique will be used for measurement of the subject's muscle strength. This technique has been used to safely obtain a quick and accurate measurement of muscle strength in young and elderly able-bodied individuals as well as patient populations⁷¹⁻⁷³. For this technique, while the subjects are generating their maximal contraction force volitionally, a supra-maximal burst of electrical stimulation (100-Hz frequency, 100-ms duration, 600 μ s pulse duration) will be delivered to the muscle. The force generated by the muscles will be recorded via a force dynamometer. The 'true' force generating ability of the muscle will be calculated as the total force generated by the subject's volitional contraction and the superimposed electrical stimulation. The maximal contraction will be repeated 2 times for each leg.

3) **Cardiac Exercise Stress Test:**

After confirming the subject's eligibility for participation in the study and clinical testing, if the subject is part of Cohort 1 that will participate in the intensive 18-sessions of gait training, the subject will be referred for a cardiac exercise stress test (treadmill exercise test). The exercise stress test will be conducted under the supervision of a cardiologist at Emory University (referral will be provided as part of this research protocol). The stress test will help confirm that the subjects who participate in the intensive gait training

treatment sessions have sufficient cardiovascular health to participate in a treadmill exercise intervention. If a participant is unable to complete the stress test due to musculoskeletal impairments or other factors unrelated to cardiac health (e.g. muscle weakness, ankle instability, inability to walk at sufficiently fast speed or incline due to post-stroke muscle weakness), then the tolerance and appropriate dosage for treadmill training will be determined based on consultation with the cardiologist, exercise physiologist, and physical therapists.

4) Procedures for Gait Training Sessions:

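### The only written-clearance rule names Cohort 2, but the fixed 18-session programme it describes belongs to Cohort 1

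*Combined protocol and SAP*

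**What the plan says.** The combined protocol and SAP has one rule on written physician clearance, under Medical Clearance in section 5 (item 1). It reads: "If a subject shows interest in participation in cohort 2 of the study (18 training sessions), before participation, we will obtain written medical clearance". The clearance is to come from the participant's own doctor, on an attached form.

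The cohorts are defined elsewhere. The Abstract describes measurements "through the course of 18 sessions of gait retraining (Cohort 1"). Section 4 says: "Within Cohort 1 (stroke and able-bodied), 25 subjects will receive identical treatment throughout the training sessions", and Aim 1 gives that cohort 18 sessions. For the other cohort, section 4 says: "Subjects in Cohort 2 can participate in 1 to 18 gait training sessions". The lead-in to H4 adds that, for Cohort 2, "we will analyze short-term changes induced by 1-3 sessions of gait retraining".

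Cohort 1 has its own cardiac screen, an exercise stress test supervised by a cardiologist. Section 5, item 3 says: "if the subject is part of Cohort 1 that will participate in the intensive 18-sessions of gait training, the subject will be referred". If the test cannot be completed for reasons unrelated to cardiac health, tolerance and training dose "will be determined based on consultation with the cardiologist, exercise physiologist, and physical therapists".

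For an overview by cohort, section 5 directs the reader to a figure: "Please see the adjoining flowchart for a summary of the procedures that subjects in each study cohort will undergo". Neither that flowchart nor the clearance form was available for this review.

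**The concern.** The clearance sentence joins a cohort number to a session count that describes the other cohort. Staff reading it cannot be sure who needs the form: Cohort 1, all of Cohort 2, or only Cohort 2 participants who do 18 sessions.

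This is a pre-entry safety rule, so the label decides what is done. On the literal text, people entering the programme that the protocol itself calls intensive need no written clearance from their own physician, while a Cohort 2 participant attending one session might. What is at stake is one safeguard for participants. Power, alpha and the analyses are not involved.

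**Working it through.** The plan gives no figure to reproduce here. The check sets the text on cohorts, session counts and pre-entry requirements side by side.

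**Which cohort has the 18-session programme**

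| Place | Cohort | Sessions |
|---|---|---|
| Section 2, Abstract | 1 | 18 |
| Section 4, Aim 1 and lead-in to H1–H3 | 1 | 18 |
| Section 5, item 3, stress test | 1 | 18, called intensive |
| Section 5, item 4, gait training | 1 | all 18, same training type |
| Section 5, Risks | 1 | 18 |
| Section 4, Objectives | 2 | 1 to 18 |
| Section 4, lead-in to H4 | 2 | 1–3 analysed |
| Section 5, item 4, gait training | 2 | one clause refers to each of the 18 sessions |
| Section 5, item 1, Medical Clearance | 2 | 18, stated as if fixed |

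Five parts of the document tie the fixed 18-session programme to Cohort 1. The clearance rule stands alone in using 18 sessions to identify Cohort 2. The 1–3 sessions under H4 describe what is analysed, not how many sessions a person may attend, so that row is weak evidence.

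**Who must have written clearance.** Cohort 2 is named once, in item 1. Cohort 1 is named nowhere in the available text.

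**Possible meanings of the sentence**

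1. It means Cohort 1: the cohort number is wrong.
2. It means all of Cohort 2: the bracketed 18 conflicts with the range of 1 to 18.
3. It means only Cohort 2 participants doing 18 sessions: it does not say so.

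The sentence needs correcting under each meaning. Under the second and third, Cohort 1 still has no clearance rule.

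**What else protects Cohort 1**

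- The stress test, or the consultation fallback when it cannot be completed for non-cardiac reasons (section 5, item 3).
- Heart-rate and blood-pressure stopping rules during sessions (section 5, item 4 and Risks).
- For stroke participants, eligibility limits on cardiovascular health, resting heart rate and resting blood pressure (section 6).

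The stress test does not cover quite the same ground as clearance. Clearance is due before participation. Item 3 most naturally places the stress test after clinical testing, which may include the 6-minute walk; item 2 also determines the fastest treadmill speed over a 4-minute bout. The consultation fallback does not name the participant's own physician. In addition, item 3 refers any Cohort 1 subject for the test, whereas Risks mentions stroke subjects only, so the position of able-bodied Cohort 1 participants is less clear.

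**How many people**

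- Planned Cohort 1 size in section 4: 25. At one clearance each, 25 × 1 = 25.
- Section 4 also assigns 45 able-bodied + 55 stroke = 100 people to the two cohorts.
- The stated cohort sizes give 25 + 25 = 50, leaving 100 − 50 = 50 people whose cohort those two figures do not settle.
- In the other direction, section 4 lets a person do both cohorts in sequence, and anyone who did Cohort 2 first could already have clearance.

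So 25 is a planning figure that could be too low or too high.

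**The case against.** The best defence is that the sentence can be read as written. Cohort 2 may run to 18 sessions, and section 5, item 4 has a clause on Cohort 2 training during each of the 18 sessions. A coherent scheme would then be physician clearance for Cohort 2 and a supervised stress test for Cohort 1. The flowchart and clearance form could confirm that. It can also be said that the stress test is the more searching cardiac check, so little is lost.

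Part of this stands. The literal scheme is possible, so a slip is likely but not demonstrated, and the unseen attachments could show which was intended. They would not remove the conflict inside the sentence, because 18 sessions is the top of Cohort 2's range and not what defines that cohort. The stress test also limits the consequence, although its later timing and its fallback mean that it does not fully replace clearance.

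A reader might infer that Cohort 1 starts intensive training with no medical screening. The documents do not support that, given the safeguards that remain. A reader might also infer that every Cohort 2 participant ought to have clearance. If the label is a slip, nothing available shows that the sponsor wanted it for someone attending a single session.

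**Conclusion.** The point holds. The only written-clearance rule identifies its cohort by a session count that belongs to Cohort 1, and Cohort 1 is not covered by any clearance rule in the available text. A cohort-number slip is the most likely explanation. The effect of following the text literally is one missing pre-entry safeguard for the intensive cohort.

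The size is about 25 participants on the planned Cohort 1 number. It would be tempting to call that an upper bound, but section 4's 100 people across the two cohorts do not allow it. The documents also do not say how many of the 25 are stroke survivors or how many will be unable to complete the stress test.

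The conclusion assumes that the flowchart and clearance form do not already state a separate rule for Cohort 1. If they do, the safety gap closes in practice, but the sentence would then contradict them and still need correcting. This should be fixed.

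**What to change.** Reword section 5, item 1 along these lines: *A physician's written clearance will be obtained before participation for every Cohort 1 participant (18 training sessions) and for any Cohort 2 participant scheduled for up to 18 sessions.* The sponsor should confirm whether Cohort 2 participants doing only a few sessions also need clearance and, if not, state the number of sessions below which it is waived. The flowchart and the Medical Clearance form should carry the same cohort labels. As an optional tidy-up, item 3 and Risks could use the same words for who takes the stress test.

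The cost is one sentence and one extra copy of an existing form per Cohort 1 participant, about 25 on the planned size. For Cohort 2 the extra forms are none if the present rule was meant to cover the whole cohort. They would be up to about 25, on the planned size of that cohort, if it was meant only for those doing 18 sessions and the sponsor chooses to extend it to everyone.
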